NPD measurement will be performed according to standard procedures. In this aim, we will use one side of the nose for the evaluation of the function of CFTR and CaCC by measuring the potential differences by initial blocking ENaC with amiloride, then using chloride free solution and isoproterenol to evaluate CFTR function, followed by ATP to evaluate CaCC function. In the other nostril, the same experiment will be repeated as mentioned above, except that after blocking ENaC with amiloride and perfusion with chloride-free solution the CFTR will not be stimulated with isoproterenol, but ATP will be used to maximize the CaCC signal. We will adjust the way of measuring the NPD for aim 2.2 depending of the results in aim 2.1.

TGF-ß and citokines will be measured using Leukosorb, a noninvasive sampling method of the nasal mucosa as previously reported. In addition, we will obtain a small amount of nasal epithelial cells to measure TGF-ß by qPCR.

Study Visits:

V1 (Screening Visit): This will be a single visit for the purpose of determining eligibility, obtaining informed consent, and recording the necessary data will include:

- Assessment of general health status and physical examination (incl. vital signs)
- Urine pregnancy test if indicated (female, child bearing age)
- Spirometry pre- and post-bronchodilators, DL_{co}, lung volumes
- Pulse oximetry
- Review of laboratory values, or if not available: venous blood sampling to assess for renal and liver abnormalities (then the measurements will be done within a week in an additional visit), CRP
- If inclusion criteria fulfilled and no exclusion criteria found:
 - Enrollment

- Completion of respiratory questionnaires (COPD only)
- Six minute walk test (COPD only)
- BODE index calculation

V2 (week 4): This visit (and the two following ones) will only done for the groups not treated with any ARBs. This visit will occur 4 weeks (\pm 4 days) after V1.

- We will again review laboratory values (CMP, CRP), repeat urine pregnancy test if indicated (female, child bearing age).
- The following procedures will be executed:
 - Completion of respiratory questionnaires (COPD only)
 - Six minute walk test (COPD only)
 - BODE index calculation
 - NPD measurement followed by nasal fluid recovered by Leukosorb filter paper and nasal cell collection for TGF-ß

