 - Subjects will be provided with a 4-week supply of 50 mg losartan for daily use (first dose given in clinic; observation with blood pressure monitoring for 2 hours).

V3 (week 5 ± 4 days):

Telephone visit to follow up on symptoms and tolerability of medication.

V4 (week 8 ± 4 days):

- The following procedures will be executed:
 - Monitor for adverse events.
 - Completion of respiratory questionnaires (COPD only)
 - Six minute walk test (COPD only)
 - Venous blood sampling to assess for renal and liver abnormalities and CMP, CRP
 - Urine pregnancy test (if applicable)
 - BODE index calculation
 - Nasal fluid recovered by Leukosorb filter paper and nasal cell collection for TGF-ß
 - Subjects will be provided with a 4-week supply of 50 mg losartan for twice daily use (100 mg)

V5 (week 9 ± 4 days):

Telephone visit to follow up on symptoms and tolerability of medication.

V6 (week 12 ± 4 days) or Early Termination Visit:

- We will draw laboratory (CMP, CRP). Repeat pregnancy test if indicated (female, child bearing age).
- The following procedures will be executed:
 - Monitor for adverse events.
 - Completion of respiratory questionnaires(COPD only)
 - Venous blood sampling to assess for renal and liver abnormalities and CMP, CRP
 - Urine pregnancy test (if applicable)
 - Six minute walk test (COPD only)

- BODE index calculation
- NPD measurement followed by nasal fluid recovered by Leukosorb filter paper and nasal cell collection for TGF-ß

Unscheduled visit (up to 2 visits) will apply if there is a need to repeat study procedures.

Subjects are allowed to be re-screened one time as per PI discretion.

Specimen Banking

Not applicable.

Data Management

Data collected will include demographics, clinical symptoms, health-related quality of life, and pulmonary function test data. Samples to be collected include NPD measurement followed by nasal fluid and cell collection for TGF-ß. We will obtain blood for safety reasons (liver and renal function) and for evaluation of an inflammatory marker. No personal identifiers will be collected and each patient's data will be coded.

Safety Reporting

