forward will minimize this risk, so that the solution is dripping out of the nose and not in the pharynx. The perfusion rate will be set at 5 ml/min, indicating that the nose will be rinsed with very low volumes. Even in case of accidental swallowing or aspiration, there are limited risks of a severe reaction, even in a respiratory-wise impaired individual. Amiloride is a diuretic and can, when given in a higher dose, increase urine production, which is not anticipated here as the used dose is low and systemic absorption is not anticipated. Isoproterenol is a beta mimetic and can lead to tachycardia, hypertension and migraine. The dose used is low and the systemic absorption negligible. Other potential side effects include nosebleed, runny nose and coughing. For the study, a subcutaneous insertion of a butterfly needle is required, which brings a minimal risk of bruising, bleeding and infection.

Nasal fluid and cell sampling: this procedure is routine and is sometimes associated with an unpleasant feeling due to the fluid, minimal risk of aspiration of part the 5 ml of sterile saline solution, and coughing. To prevent this from happening, the head of the patient will be bend forward during the collection, so the fluid will be absorbed by Leukosorb and not get into the pharynx where it can be swallowed or aspirated. Cell sampling can cause a mild discomfort and a mild nosebleed.

Phlebotomy: The risks from blood draw from a vein are minimal but include discomfort at the site of puncture, possible bruising around the puncture site, rarely an infection, and uncommonly, fainting from the procedure. Blood draws will be performed with as much care as possible to minimize local complications. Subjects will be sitting during the process for their comfort and will be asked to not look directly at the site of blood draw.

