Appendix I

	For all	For subjects who are not on ARBs treatment				
	subjects					
	Visit 1 Screening	Visit 2 ^g 4 weeks (± 4 days) after V1	Visit 3 Phone Call 1 weeks (± 4 days) after V2	Visit 4 8 weeks (± 4 days) after V2	Visit 5- Phone Call 9 weeks (± 4 days) after V2	Visit 6 12 weeks (± 4 days) after V2
Informed Consent	X					
Assessment of health status	X	Х		Х		Х
Medical History	Х					
Occupational history	Х					
Smoking History	Х					
Concomitant medication	X		Х		Х	
Urine cotinine test	Х	Х		Х		X
AE and SAE		Х	Х	Х	Х	X
Physical exam	Х	Х		Х		Х
Vital signs	X	X		Х		Х
Urine pregnancy test ^a	Х	Х		Х		Х
β–HGC ^b	Х	X		Х		X
Complete Pulmonary function test pre and post	X					
Renal and liver blood test ^c	X	X		Х		X
CRP ^d	Х	Х		Х		X
Respiratory Questionnaires ^e	X	X		Х		X
6 Minute Walk Test ^f	Х	Х		Х		X
NPD measurement		Х		Х		Х
Nasal fluid for TGF -β measurement	X	Х		Х		Х
Drug Dispensation (losartan 50 mg or 100 mg)		Х		Х		
Drug Compliance				Х		Х

a- Only for female

b- If urine pregnancy test is positive

c- Only if results are not available on the last 6 month

d- Only if results are not available on the last 6 month

e- Respiratory Questionnaire (BCSS, MRC, Charlson co-morbidity index, SGRQ, CAT) will be performed at each visit before any study procedure (COPD group only)

f- 6MWT will be performed for participants on the COPD group only

g- Visit 1 and 2 could be combined if the subject is not on ARBs treatment and has renal and liver blood test results available on the last 6 month.

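### Nasal TGF-ß is sampled after NPD perfusion at V2 and V6 but, by the visit text, without NPD at V4; text and Appendix I disagree at V1 and V4, and no baseline visit is named

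*Combined protocol and SAP*

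**What the plan says.** **Visit text (Study Visits).** V1 is described as follows: "This will be a single visit for the purpose of determining eligibility, obtaining informed consent, and recording the necessary data". Its list covers examination, pregnancy test, lung function, oximetry, laboratory values, questionnaires, walk test and BODE. It contains no NPD, nasal fluid or nasal cells. V2 and V6 carry the same line: "NPD measurement followed by nasal fluid recovered by Leukosorb filter paper and nasal cell collection for TGF-ß". At V2 the drug supply comes next in the list: "Subjects will be provided with a 4-week supply of 50 mg losartan for daily use (first dose given in clinic". V4 lists nasal fluid and nasal cells, with no NPD.

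**Appendix I.** The row "Nasal fluid for TGF -β measurement" is marked at V1, V2, V4 and V6. The NPD row is blank at V1 and marked at V2, V4 and V6. The V1 column is for all subjects; the later columns are headed "For subjects who are not on ARBs treatment". There is no row for nasal cells. Footnote g lets V1 and V2 be combined for some subjects.

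**Elsewhere in the protocol.** The Objectives plan NPD untreated, on 50 mg and on 100 mg. Study Procedures describes NPD in one nostril and then says: "In the other nostril, the same experiment will be repeated as mentioned above". Under Risks to Subjects: "The perfusion rate will be set at 5 ml/min". For the cells, Study Procedures says: "we will obtain a small amount of nasal epithelial cells to measure TGF-ß by qPCR". Data Management again puts NPD before nasal sampling. Treatment arms makes each subject's baseline the control for later values, but does not say which visit supplies it.

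**The concern.** Inhibition of TGF-ß signalling is the mechanism that the trial rests on, and nasal TGF-ß is the direct check on it. All subjects receive 50 mg and then 100 mg, open label, and no placebo arm is described. Within-subject change therefore carries the inference. If the way the sample is obtained changes between visits, nothing in the design can separate that change from the drug.

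The sampling condition does change. After NPD, both nostrils have been perfused and no unperfused side remains; no interval between perfusion and sampling is stated. A site following the visit text samples after perfusion at V2, without it at V4, and after it at V6. A site following Appendix I has NPD on all three of those days, but also holds an extra untreated sample from V1 taken without NPD. Because no baseline visit is named, that V1 value could be used as the reference for change.

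**Working it through.** No TGF-ß effect size, variance, power or sample size is stated, so there is no planned figure to reproduce. The check sets the two schedules side by side and then traces which contrasts are affected.

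**Step 1: sampling condition by visit**

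| Visit | Visit text | Appendix I | Agree? |
|---|---|---|---|
| V1 | no nasal sample, no NPD | nasal fluid, no NPD | no |
| V2 (before first dose, by list order) | NPD, then sample | NPD and nasal fluid | yes |
| V4 (on 50 mg) | sample, no NPD | NPD and nasal fluid | no |
| V6 (on 100 mg) | NPD, then sample | NPD and nasal fluid | yes |

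Appendix I does not give the order within a visit. Data Management gives a general order, NPD first, and that order is used below for the Appendix I reading.

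**Step 2: effect on each contrast**

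Let f be TGF-ß recovered after perfusion divided by TGF-ß recovered without it. The documents give no value for f. Assume that f is the same at every visit where NPD comes first, and that the drug has no effect. The measured value is then proportional to f after NPD and to 1 without NPD. The false relative change between two visits is the ratio of the two conditions minus 1.

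| Contrast | V4 by visit text | V4 by Appendix I, NPD first |
|---|---|---|
| V2 to V4 (untreated to 50 mg) | 1/f − 1 | f/f − 1 = 0 |
| V4 to V6 (50 to 100 mg) | f/1 − 1 = f − 1 | f/f − 1 = 0 |
| V2 to V6 (untreated to 100 mg) | f/f − 1 = 0 | f/f − 1 = 0 |
| V1 to V2, if V1 is sampled | f − 1 | f − 1 |
| V1 to V4, if V1 is sampled | 1/1 − 1 = 0 | f − 1 |
| V1 to V6, if V1 is sampled | f − 1 | f − 1 |

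**Step 3: reading the table**

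- If f = 1, there is no artefact anywhere.
- If f < 1 and the V4 text is followed, TGF-ß appears to rise on 50 mg and fall on 100 mg. If f > 1, the pattern reverses.
- The two V4 artefacts cancel over the whole study, since (1/f) × f = 1. That is why V2 to V6 is clean.
- With V2 as baseline, the remaining problem comes only from the V4 text. With V1 as baseline, V6 is always mismatched.
- For subjects whose V1 and V2 are combined, the choice between V1 and V2 largely disappears. The V4 problem does not.

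**The case against.** The strongest reply is that a sound baseline already exists. At V2 the text and Appendix I agree, the sample precedes the first dose in the list, and the wording matches V6. No section makes V1 the baseline. This stands. A reader might infer that nasal TGF-ß has no usable baseline, or that a V1 value is comparable with nothing later; neither follows. V2 is usable but not designated, and under the V4 text a V1 sample would match V4.

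Second, a perfusion effect is not shown. The Risks section calls the volumes very low, no perfusion time is given, and the nasal sampling itself uses 5 ml of saline, so that sample is wet too. A reader might infer that perfusion washes TGF-ß out and so imitates suppression by losartan, and might attach a percentage to it. The documents support neither the direction nor any percentage. For qPCR on cells an effect is less clear than for fluid. What remains is that an uncontrolled change of condition is avoidable and could not be corrected afterwards.

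Third, NPD, not TGF-ß, is the stated outcome variable. That limits the weight of the point. The V4 conflict, however, also decides whether any NPD is obtained on 50 mg, which the Objectives require.

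Fourth, the missing nasal-cell row might suggest that the cells would never be collected. The V2, V4 and V6 text, Study Procedures and Data Management all call for them, so this is a gap in the table only.

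Finally, V1 samples share one condition across groups and could serve a between-group description. That stands, and the fix allows for it.

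**Conclusion.** The point holds as an inconsistency in sampling conditions with a definite list of affected contrasts. Following the visit text, the untreated-to-50 mg and 50-to-100 mg comparisons of nasal TGF-ß each set a post-perfusion sample against one taken without perfusion. If the V1 sample in Appendix I is taken, V1–V2 and V1–V6 have the same mismatch. V2–V6 is unaffected, provided any perfusion effect is the same at both visits.

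The size is unknown: it is f − 1 or 1/f − 1, and the documents give no f. The conclusion therefore rests on the possibility that perfusion of both nostrils alters what is recovered in nasal fluid. That is plausible from the procedure described but not established in the documents. The disagreements between text and Appendix I at V1 and V4, the unnamed baseline visit and the missing nasal-cell row need no assumption.

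**What to change.** 1. Reconcile the V4 text with Appendix I and the Objectives so that NPD is done at V4.
2. State one order of nasal sampling relative to NPD and apply it at V2, V4 and V6. NPD first is already the order in the V2, V6 and Data Management text.
3. Name the V2 sample, taken before the first dose, as the baseline for TGF-ß and cytokines.
4. Resolve the V1 mark in the nasal fluid row: delete it, or label it descriptive only (for example for comparing groups) and never the reference for change. Where V1 and V2 are combined, say that the single sample follows the V2 order.
5. For consistency, add a nasal-cell row to Appendix I at V2, V4 and V6.

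**Cost.** The edits are to wording and the table. Compared with the V4 text alone, the change means one NPD session per subject at V4; Appendix I already schedules that session and the Objectives already require it. If the V1 mark is deleted, one untreated sample per subject is lost, and it was not taken under the same conditions as V2 and V6.

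### A 4-week losartan supply without overage and a ± 4-day visit window can leave a fully adherent subject off drug when measured, and Appendix I misplaces the visits

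*Combined protocol and SAP*

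**What the plan says.** The Objectives section wants NPD repeated while the subject is taking each dose, and Treatment arms places the re-evaluation at the close of each four-week step.

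Under Study Visits, drug is handed out twice:

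- V2: "Subjects will be provided with a 4-week supply of 50 mg losartan for daily use", with the first dose taken in clinic that day.
- V4: "Subjects will be provided with a 4-week supply of 50 mg losartan for twice daily use (100 mg".

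The visits that end the two steps are "V4 (week 8 ± 4 days" and "V6 (week 12 ± 4 days) or Early Termination Visit", with V2 at week 4. Appendix I marks dispensing at V2 and V4 only. No overage, interim resupply or instruction to keep dosing until the visit is stated. Unused drug is returned, and Appendix I lists a compliance check at V4 and V6.

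The Appendix I column headers give different timing: "Visit 4 8 weeks (± 4 days) after V2" and "Visit 6 12 weeks (± 4 days) after V2". Footnote g of that table also allows V1 and V2 to be combined.

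**The concern.** The quantity dispensed equals the nominal interval between visits, but the window lets the interval run longer. A subject can follow the protocol exactly, attend late but in window, and have no tablets left before the measurement. TGF-β sampling is exposed at V4 and V6. NPD is exposed at V6 and, according to Appendix I, at V4; the V4 visit text lists no NPD.

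The V4 and V6 values are compared with each subject's own untreated baseline and read as the losartan effect. If the effect wanes within days of stopping, a value taken after run-out understates it, and unequal gaps at V4 and V6 would also distort the comparison of 50 mg with 100 mg. If the effect outlasts the gap, little is lost.

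The Appendix I headers add a second problem. A coordinator who books visits from that table would put V4 about four weeks after the first supply ended.

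**Working it through.** **Inputs.** Supply per step is 4 weeks = 28 days (Study Visits, V2 and V4). Visit weeks are 4, 8 and 12, each ± 4 days (Study Visits). The Appendix I headers put V4 and V6 8 and 12 weeks after V2. Let a, b and c be the deviations in days of V2, V4 and V6, each from −4 to +4.

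**The plan's own figure.** The visit text gives (8 − 4) × 7 = 28 days from V2 to V4 and (12 − 8) × 7 = 28 days from V4 to V6, which reproduces four weeks per step. Appendix I gives 8 × 7 = 56 days from V2 to V4, which does not.

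**Gap.** Count the dosing days missed before the visit day by a subject who takes every tablet: gap = max(0, interval − 28). For example, with the clinic dose on day 0 as the first of 28, the last dose is on day 27. A visit on day 32 then follows missed doses on days 28, 29, 30 and 31, a gap of 4.

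| Reading of the schedule | V2 to V4 (days) | Gap at V4 | V4 to V6 (days) | Gap at V6 |
|---|---|---|---|---|
| A. Window from the previous visit | 28 + b = 24–32 | at most 4 | 28 + c = 24–32 | at most 4 |
| B. Each visit floats around its week from V1 | 28 + b − a = 20–36 | at most 8 | 28 + c − b = 20–36 | at most 8 |
| C. V2 as day 0, V4 at 4 weeks, V6 at 8 weeks | 28 + b = 24–32 | at most 4 | 28 + c − b = 20–36 | at most 8 |
| D. Appendix I read literally | 56 + b = 52–60 | 24–32 | 28 + c − b = 20–36 | at most 8 |

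Under B the two gaps together cannot exceed 8: if both steps overrun, the sum is (b − a) + (c − b) = c − a, at most 8. If the clinic dose is not taken from the dispensed supply, the step 1 maximum falls by one day, to 3 under A and 7 under B.

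The 24–32 day gap in row D also arises under the visit-text week numbers if V1 and V2 are combined and weeks are still counted from V1.

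**Is Appendix I a labelling error?** Its phone-call header, "Visit 3 Phone Call 1 weeks (± 4 days) after V2", agrees with "V3 (week 5 ± 4 days" when V2 is at week 4. The V4, V5 and V6 headers instead reuse the visit-text week numbers 8, 9 and 12 and count them from V2. Safety Reporting describes the study as lasting three months. The visit text gives 12 weeks = 84 days (2.8 months) from V1 to V6; the literal headers give 4 + 12 = 16 weeks = 112 days (3.7 months) when V1 and V2 are separate. Both comparisons point to study weeks from V1 wrongly labelled as weeks from V2.

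**The case against.** The strongest reply is that the shortfall is read from silence. The protocol gives no tablet count, the drug is a commercial product kept at the site and handed over by study staff, and they could match the quantity to the booked visit. A gap also needs near-perfect adherence and a late visit; a missed dose leaves a spare tablet. On-time and early visits under the visit text are covered, unless weeks are counted from a combined V1/V2. No offset time is given, so no bias is shown, and understating an effect does not create a false positive. The largest figures need staff to follow headers that look mislabelled, or one visit at its earliest limit and the next at its latest. The three-month argument fails if V1 and V2 are combined, because the literal headers then also give 12 weeks.

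Much of this stands, and it keeps the point minor. It does not remove it. Nothing in the text requires spare tablets, and following the stated supply and window exactly can produce the gap. Returned drug and the compliance check, together with the dispensing and visit dates, can reveal run-out, but only after the measurement. The phone-call header still identifies the anchor error without the three-month argument.

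Two remarks on the remedy are also fair. Ending the window at day 28 gives up its whole late half. And 28 doses from day 0 leave none for the morning of a day-28 visit. That is not a gap as defined here, but it matters if a dose is wanted on the visit day.

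**Conclusion.** The concern holds and is minor. As written, a fully adherent subject attending in window can be off drug at an endpoint visit. The gap is at most 4 dosing days if windows run from the previous visit and at most 8 if visits float around study weeks. It is 24 to 32 days at V4 if Appendix I is followed literally.

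These figures assume exactly 28 days of supply, full adherence and no informal overage. How often visits run late and how fast the effect fades are not in the documents, so neither the number of affected values nor the size of any bias can be stated. The Appendix I headers conflict with four-week dosing on any reading and need correcting, but that correction alone leaves the supply shortfall in place.

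**What to change.** 1. Correct Appendix I so that V4 is 4 weeks after V2, V5 is 1 week after V4 and V6 is 4 weeks after V4. Use the same anchors in the visit text, including when V1 and V2 are combined.
2. Preferably, close each window by day 28 after dispensing, for example −4/+0 days. Intervals are then 24–28 days and the gap is 0. The cost is tighter scheduling, since late visits would become deviations.
3. Otherwise, keep ± 4 days from the previous visit and dispense 32 days per step: 32 × 1 = 32 tablets and 32 × 2 = 64 tablets of 50 mg, against 28 and 56. That is 4 and 8 extra tablets per subject. The gap is 0, but a step may run up to 4 days past four weeks. If visits were left floating around fixed study weeks, 36 days (36 and 72 tablets) would be needed.
4. Under either option, tell subjects to continue the assigned dose up to the measurement visit, and record the date of last intake at V4 and V6 so that any value taken after run-out can be flagged. If a dose is wanted on the visit day itself, add it to the supply.

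Beyond the scheduling or tablets, the cost is the corrected headers and one case report form field. Unused drug is already returned and counted.

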- Acute pulmonary exacerbation within 6 weeks from the Screening Visit.
- Subjects with no airflow obstruction by spirometry but with a decrease in DLco < 70% possibly indicating emphysema.
- Significant exposure to environmental tobacco smoke or atmospheric or occupational pollutants for the non-smokers group.
- Urine pregnancy positive test at the Screening Visit.

Treatment arms

Patients will be given four weeks of 50 mg of losartan daily and consequently an additional four weeks of 100 mg of losartan (divided in two doses of 50 mg twice daily). This higher losartan dose was used safely in other clinical trials (www.clinicaltrials.gov; search: losartan and COPD). At the end of each four-week period, participants will be re-evaluated. We will compare treatments using baseline measurements of each individual as his/her own control.

Study Drug:

Cozaar[®], the commercial form of losartan will be obtained from the UMHC Pharmacy and given to the subjects by the PI or study coordinators free of charges. FDA has granted IND exemption for this study. Study drug will be stored as per package instructions in a locked cabined on the research room at UMH 6th floor west room 607. Only the study team has access to this room. The storage area at the study center will be monitored by the staff for temperature consistency with the acceptable storage conditions.

The Investigator is responsible for maintaining accurate study drug accountability records throughout the study.

Each dispensing of study drug will be documented in the subject's study records and in the drug accountability log. Subjects will return all unused study drug for drug accountability. Study drug will be destroyed at the clinical site as per the Institution regulations.

Study Procedures

Once informed consent is signed, the subjects will have an initial visit during which they will have a physical exam (including vital signs), complete study questionnaires and PFTs. All study subjects will undergo the following procedures during a single visit:

History and physical examination will be performed including vital signs and body mass index (BMI) will be recorded.

Laboratory Samples: Urine will be collected for a pregnancy test if applicable and blood test for CMP and CRP will be drawn, if results are not available within 6 months of the Screening visit.

Urine cotinine levels will be measured at the time of study visits to assess smoking status (active or not).

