Treatment with losartan: Cozaar ® is an FDA-approved ARB widely prescribed for treatment of hypertension, heart failure, and for renal protection in patients with diabetes. The doses proposed in this study are well tolerated by non-hypertensive patients without significant effect on blood pressure. The most common side effects are fatigue and dizziness. Serious adverse events that are rare include angioedema, hypotension, renal dysfunction or failure, blood dyscrasias, hepatitis, or rhabdomyolysis (clinical assessment of muscle pain). The following should lower the risks to the subjects: The first dose of medication will be administered in the clinic and the patient observed for two hours with blood pressure monitoring every 30 minutes. If systolic blood pressure falls below 100 mmHg, the patient will be discharged from the study and dosing not repeated.

If the patient has symptomatic hypotension, the patient will be put into a supine position until recovered. If needed additional interventions will be undertaken (including button limited to fluid administration) according to the supervising physician's instructions.

Subjects with hyperkalemia, renal dysfunction, or who are taking potassium supplements will not be enrolled into the study. Participants will be given at the screening visit written descriptions of potential side effects and participants will be instructed to contact the study doctor if any new symptoms occur. Skin rashes, palpitations or other moderate or severe adverse events (interference with usual daily activities) without other clear explanation should warrant immediate cessation of treatment and notification of study personnel.

Six Minute Walk Test: the participant walks for six minutes and the distance traveled is measured. As with any exercise test, there is a theoretical risk but in multiple clinical trials conducted at our site, we had no adverse events. Risks are minimized by medical supervision and trained medical personnel.

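### V4 draws the first on-treatment safety bloods and dispenses 100 mg/day with no required review in between, and Appendix I footnotes c and d waive V4 and V6 bloods that the visit text orders

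*Combined protocol and SAP*

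**What the plan says.** **Dose step (Study Visits).** V2 includes a laboratory review, "We will again review laboratory values (CMP, CRP", and then gives the first 50 mg dose in clinic with two hours of blood-pressure observation. V3 is a telephone call about symptoms and tolerability. V4 (week 8) lists "Venous blood sampling to assess for renal and liver abnormalities and CMP, CRP" and, further down the same list, "Subjects will be provided with a 4-week supply of 50 mg losartan for twice daily use (100 mg". V5 is another telephone call. At V6 (week 12) the text says "We will draw laboratory (CMP, CRP".

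**General safeguards.** Treatment arms says "At the end of each four-week period, participants will be re-evaluated". Appendix I marks health status, adverse events, physical exam, vital signs and drug compliance at V4. Data Management says that blood is taken for liver and renal safety. Adverse Event Monitoring makes clinically relevant laboratory abnormalities reportable, and Removal of Subjects provides for withdrawal.

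**The 6-month rule.** Under Laboratory Samples, blood is drawn at entry "if results are not available within 6 months of the Screening visit". Appendix I marks the renal and liver row at V1, V2, V4 and V6 and attaches to the whole row: "c- Only if results are not available on the last 6 month". Footnote d puts the same condition on the CRP row.

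**Recognised risk.** The losartan risk section states: "Serious adverse events that are rare include angioedema, hypotension, renal dysfunction or failure, blood dyscrasias, hepatitis, or rhabdomyolysis". It also bars subjects with hyperkalemia or renal dysfunction from enrolling.

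**The concern.** The plan reviews chemistry before the first dose but has no matching step before the dose is doubled. The changes that matter here (potassium, creatinine, liver tests) can be symptomless, so a physical exam, vital signs or a call about tolerability need not reveal them. The blood test is the safeguard for that purpose, and nothing in the text says it must be read before the step it should inform.

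The pre-treatment comparator may also be old. Results up to 6 months old are accepted at entry, and Appendix I footnote g lets V1 and V2 be combined on the strength of such results. For some subjects V4 would be the first fresh chemistry in months.

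The footnotes add a second route to the same gap. Staff working from the schedule table could decide that a subject with a recent result needs no bloods at V4 or V6, and so skip the on-treatment test altogether.

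**Working it through.** The plan has no figure of its own to reproduce here. The check is a reading of the visit sequence followed by date and tablet arithmetic.

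**1. Sequence of laboratory contact and dosing**

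| Visit | Bloods | Stated review of results | Dosing |
|---|---|---|---|
| V2 | values reviewed | yes | first 50 mg |
| V3 | none (telephone) | no | 50 mg daily |
| V4 | drawn, no condition | no | 100 mg/day dispensed |
| V5 | none (telephone) | no | 100 mg/day |
| V6 | drawn, no condition | no | end |

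V4 is the first scheduled on-treatment chemistry. No section makes the step wait for it, sets an on-treatment potassium or creatinine limit, or gives a date by which it must be read.

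**2. Exposure before the result is known**

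The documents give no laboratory turnaround t, so I assume 1 to 3 days and prompt reading. Extra drug is (2 − 1) × t, which is 1, 2 or 3 tablets of 50 mg. A same-day result read before dosing gives 0. Because no reading date is required, 1 to 3 is not an upper bound. If the result went unread until V6, the nominal figure would be 28 days × 1 = 28 tablets. That is the outer limit of what the text permits, not an expectation. The point applies to every subject reaching V4: 30 by Recruitment Methods, or 10 + 20 + 20 = 50 by the Study Population groups. No rate of abnormal results on 50 mg is given, so I claim no count of affected subjects.

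**3. Footnote c read literally**

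Take 6 months as 182 days, use nominal visit days counted from V1, and let each new draw restart the clock. A test is due only when the last result is more than 182 days old. The table gives the age of the qualifying result at V1, in days.

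| Schedule | No draw at V2, V4 or V6 | V6 only | V4 only | V2 only (pre-dose) |
|---|---|---|---|---|
| Visit text (V2 28, V4 56, V6 84) | 0–98 | 99–126 | 127–154 | 155–182 |
| Appendix I clock (28, 84, 112) | 0–70 | 71–98 | 99–154 | 155–182 |
| V1 and V2 combined (0, 28, 56) | 0–126 | 127–154 | 155–182 | none |

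A subject whose bloods are drawn at screening falls in the first column on every schedule. The first and last columns together are the ages with no on-treatment test: 99 + 28 = 127 of 183 possible ages (69%) on the visit-text schedule, 71 + 28 = 99 of 183 (54%) on the Appendix I clock, and 127 of 183 (69%) with combined visits. Result ages are not given. If they were spread evenly, these would be the shares of subjects with an existing result, and those drawn at screening would add to them. On that assumption, most subjects would need no on-treatment renal or liver test.

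**4. Does holding the step fit the schedule?**

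Visit days are V4 = 56 ± 4 (52 to 60), V5 = 63 ± 4 (59 to 67) and V6 = 84 ± 4 (80 to 88).

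- The V4–V6 gap already runs from 80 − 60 = 20 to 88 − 52 = 36 days, nominally 28.
- Days at 100 mg with a hold of t days are 28 − t = 27, 26 or 25 (96%, 93%, 89% of 28). At the shortest gap they are 20 − t = 19, 18 or 17.
- The latest step is day 60 + 3 = 63, and V5 can be made up to day 67, so the call can always follow the step.
- Tablets needed over a gap of L days are 2L − t. At L = 28 this is 53 to 55, within the 56 supplied. At L = 36 it is 69 to 71, which 56 does not cover. The plan without a hold needs 72 there, so that shortfall exists already.

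**The case against.** The strongest reply is that the protocol does not say the result goes unread. V4 lists the blood draw before the dispensing line, gives neither a turnaround nor the hour of the first 100 mg dose, and the blood is expressly taken for safety. This stands. A reader might infer that subjects following the plan would double the dose with an unread result, and the text supports only that they could. The allowance at V1 of up to a week for missing measurements is not evidence of a slow laboratory either, since it concerns arranging an extra visit.

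A second reply is that physicians monitor continuously, relevant abnormalities are reportable and followed up, and subjects put at unnecessary risk must be withdrawn. These provisions let the investigator act on a late result, which limits the harm, but none of them makes the step wait.

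Third, the risk is small. The exclusion criteria remove ACE inhibitors, aliskiren, potassium supplements, regular NSAID use, renal artery stenosis, and renal or hepatic disease judged to interfere. The protocol describes the doses as well tolerated and the higher dose as used safely in other trials. This also stands and bears on the weight of the point. It does not supply the missing sequencing sentence.

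On the footnotes, a reader might infer that the trial plans to skip on-treatment chemistry. The documents do not support that. The visit text orders the V4 and V6 bloods without condition, and the body's 6-month rule is tied to Screening, so the waiver is probably a drafting slip. The table still contradicts the text.

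**Conclusion.** Two points hold. First, the first on-treatment safety bloods coincide with dispensing of the doubled dose, and no rule requires review in between, so escalation before a symptomless abnormality is read is possible. Second, footnotes c and d contradict the visit text and, taken literally, remove on-treatment renal, liver and CRP testing for many subjects. The footnote slip is a separate drafting matter and does not make the dosing gap more serious.

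The absolute risk is probably low. The 1 to 3 tablet figure rests on an assumed turnaround and prompt reading. The claim that most subjects would escape on-treatment testing rests on a literal reading of the footnote and an even spread of result ages. Nothing here touches power, alpha or the V4 measurements, which are taken before the step. The point is worth correcting because the plan treats these risks as real and the correction is cheap.

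**What to change.** **1. Review before the step.** Add to V4 that the investigator reviews the V4 CMP before the first 100 mg/day dose. Any of three routes would do:

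- a same-day result;
- a draw shortly before V4, within its existing window;
- dispensing at V4 with 50 mg once daily continued until a telephone call confirms the step.

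Do not step up with hyperkalemia, renal dysfunction, or LFTs above 3 times the upper limit (the figure in the exclusion criteria). The protocol gives no limits for the first two. The investigator must write in a potassium ceiling and a maximum creatinine rise from the pre-treatment value, because the rule is incomplete without them. If a limit is exceeded, repeat the test at an unscheduled visit (up to 2 are allowed) or withdraw the subject. Keep V6 on schedule, make the V5 call after the step, and record the step date.

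**2. Footnotes.** Restrict both c and d to V1 and V2, so that V4 and V6 bloods, including CRP, are always drawn.

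**Cost.** A same-day result costs almost nothing. A draw before V4 adds an attendance. The hold adds one call per subject: at the protocol's $25 per call, 25 × 30 = $750 or 25 × 50 = $1,250. It also takes about 1 to 3 days from the period at 100 mg, less than the ±8 days the visit windows already allow. A twice-daily supply taken once daily at first carries some risk of dosing error, so the hold needs a written instruction with the pack. Repeat visits, at $50 each, arise only for subjects over a limit.
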